Exclusion criteria: Patients with clinical evaluation of high-risk pregnancies will be excluded, including chronic hypertension, diabetes mellitus, obesity, multiple pregnancies, severe COVID-19 infection, previous thromboembolic event, acute or chronic hematological events (eg, thrombus formation isolated to thrombophilia), use of anticoagulants, cardiovascular disease, lung disease, kidney disease, immunosuppression, severe mental disorder, recurrent abortion, previous premature birth, previous or current cancer.

Sample size and power calculation

The sample size calculation was based on the primary outcome - difference between scores on the GAD-7 anxiety scale -, compared to means, estimated at 4 points, and standard deviation of 4 points. A sample of 26 patients each group is needed to have 80% power, at the 5% significance level; considering losses of 15% in the follow-up, the final size of the intended sample will be 60 patients. Recruitment will continue until target sample size is reached. The sample was calculated using the formula for superiority randomized clinical trials proposed by WANG et al., 2017 (Figure 1):

$$n_1 = \left\lceil \frac{(z_\alpha + z_\beta)^2 (\sigma_1^2 + \sigma_0^2 r)}{(d - \delta)^2} \right\rceil,$$

$$n_0 = \left\lceil \frac{(z_\alpha + z_\beta)^2 (\sigma_1^2 / r + \sigma_0^2)}{(d - \delta)^2} \right\rceil.$$

Figure 1: formula for superiority randomized clinical trials.

Recruitment

The recruitment population includes pregnant women presenting for their first antenatal visit at 6 to 12 weeks of gestation. Participation in the study will be followed until completion of the postpartum period.

Eligible participants will receive information about study design, objectives, risks and benefits in adapted language, participant information leaflet and participant consent form (Appendices).

Randomisation

The randomization process in this RCT will use random permuted blocks to ensure similar numbers of participants in each intervention arm throughout the trial and

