Clinical outcomes will be collected to explore the clinical effectiveness of the TPC based on hospital database reviews (Chart 5).

Chart 5: Maternal-fetal outcome and puerperal aspects

Maternal-fetal outcome and puerperal aspects	
Delivery methods	Vaginal or cesarean
Gestational age at birth	preterm, term, post term
Maternal complication	Infectious, hemorrhagic, none, other
Newborn's size	Small, appropriate, large for gestational age
Need for neonatal ICU	Yes or No
Breast-feeding	Yes or No; time and reason
Need to return to obstetric emergency	Yes or No; reason
Need for medical appointments in pediatric emergency	Yes or No; reason

Outcomes

Primary outcome: Mean between-group differences in GAD-7 scores.

Secondary outcome 1: difference between means, between groups, of data related to the mother: delivery mode and obstetric complications.

Secondary outcome 2: difference between means, between groups, of data related to the baby: gestational age at birth, birth weight, APGAR, neonatal intensive care unit (ICU) admission.

Secondary outcome 3: economic analyses.

The quality of assistance will be evaluated by the Humanization Program for Prenatal and Birth (PHPN) criteria proposed by Brazil Ministry of Health (21). Adherence to the proposed care will be assessed by attending the consultations, carrying out the proposed exams and extra consultations in the Obstetric Emergency. The schedule intervention was present at Figure 2.

Figure 2: Flow Chart of recruitment, intervention and evaluations

Figure 1: Flow Chart of recruitment, intervention and evaluations								
MOMENT	Study period							
	Screening	Allocation	Post Allocation				Finalization	
-t1	0		t1	t2	t3	t4	t5	t5
RECRUITMENT								
Eligibility evaluation	X							
ICF *		X						
Allocation		X						
INTERVENTION								
SG and GC: In-person queries			X	X	X	X		
SG: Telemedicine consultations			X	X	X	X		
EVALUATION								
Sample ascription	X							
Anxiety (GAD-7)			X	X	X	X		
LQ and costs (E5-5D)			X	X	X	X		
Personal costs								
Implementation costs							X	
Clinical Outcomes							X	
Feasibility								X
Accession								X
Quality (PHN)								X
Cost-effectiveness								X

Legend

t1 Initial eligibility evaluation through referral to the PN
 T0 Allocation based on eligibility criteria
 t1 First Trimester
 t2 Second trimester
 t3 Third trimester
 t4 Puerperium

Analysis plan

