This RCT will have an analysis by intention-to-treat and per protocol (at least 6 sessions attended) since it is an RCT of effectiveness. The primary outcome will be analyzed by generalized linear models of mixed effects (GLMM) or by generalized estimation equations (GEEs). Adjustments for confounding or baseline variables may be made if justified. Secondary outcomes can be analyzed in 2-test linear models using the Mantel-Hanszel test, linear trends for ordinary categorical variables or multivariate regression models for categorical variables. For repeated measures, the same analysis of the primary outcome (GLMM or GEEs) will be maintained. The

level of significance for the statistical tests conducted will be 5% and effect estimates will be presented with 95% confidence intervals.

The cost-effectiveness and cost-utility analysis will be carried out following the intention-to-treat principle according to the randomized clinical trial dataset (22) in software R. The differences in cost and effect will be estimated using a set of equations of apparently non-correlated regressions, which adjusts the model to correlate costs and effects and also allows adjustment for potential confounding factors. The incremental cost-effectiveness ratio (ICER) will be calculated by dividing the difference in costs between interventions by the difference in effect between interventions. Bias-corrected accelerated bootstrapping with 5000 replications will be used to estimate uncertainty around costs and effects. The cost-effect pairs, results of 5000 bootstrapping replications, will be plotted in cost-effectiveness plans (CE-plan) (23). The cost-effectiveness acceptability curves (CEACs) will be estimated to show the probability that the intervention will be cost-effective compared to the control, in different amounts of willingness to pay (that is, the amount in Reais that the health system is willing to pay per unit of effect won) (23). Multiple imputation will be used to predict missing data. The data imputation model will include variables associated with the missing data (24).

Data protection and participant confidentiality

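### The secondary-outcome measure, a difference between means, has no meaning for the four unordered complication categories, and the Analysis plan assigns no effect measure or sparse-data rule to the binary outcomes.

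*Combined protocol and SAP*

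**What the plan says.** The Outcomes section gives one measure for all clinical secondary outcomes. Secondary outcome 1 is "difference between means, between groups, of data related to the mother: delivery mode and obstetric complications". Secondary outcome 2 is "difference between means, between groups, of data related to the baby: gestational age at birth, birth weight, APGAR, neonatal intensive care unit (ICU) admission".

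Chart 5 shows the scale on which these are recorded. Delivery is "Vaginal or cesarean", maternal complication is "Infectious, hemorrhagic, none, other", gestational age at birth is "preterm, term, post term", and neonatal ICU need is yes or no. Birth weight and APGAR are not listed in the chart.

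The Analysis plan does not repeat the difference between means. It gives a permissive list of methods for secondary outcomes, "using the Mantel-Hanszel test, linear trends for ordinary categorical variables" or "multivariate regression models for categorical variables", and promises effect estimates with 95% confidence intervals. It does not say which method goes with which outcome, which effect measure is estimated, what link the regression uses, or what happens when events are few. The Abstract describes the allocation as unstratified.

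**The concern.** A mean needs numbers, or at least a 0/1 code. Maternal complication is neither, so the stated measure for that outcome cannot be interpreted. The Analysis plan does not repair this, because the analyst would still have to choose the test and the measure after seeing the data.

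The trial is also small for clinical events and excludes high-risk pregnancies. If a complication type or ICU admission is rare, an arm with no events is likely, and an odds ratio from logistic regression is then zero, infinite or undefined, with no usable Wald interval. The Discussion aims at similar effectiveness with no loss of quality of care, and these outcomes are the clinical evidence for that. A model that fails, or a non-significant test, is easily reported as no difference. The reader needs the absolute difference and the size of harm that the data still allow.

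**Working it through.** **Inputs.** The sample-size section states "A sample of 26 patients each group is needed to have 80% power". With 15% losses it arrives at 60 in total: 52 × 1.15 = 59.8, so 30 per arm randomised. The 26 does not follow from the stated difference of 4 and SD of 4: 2 × 4² × (1.960 + 0.842)² / 4² = 15.7, or 16 per arm two-sided. That is a separate matter; 26 and 30 are used here simply as the planned numbers. The documents give no event rates, so rates of 3% to 20%, equal in both arms, are assumed.

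**1. Mean of unordered codes.** Take 26 women per arm with these illustrative counts of none / infectious / hemorrhagic / other: 20 / 3 / 1 / 2 in arm A and 20 / 1 / 3 / 2 in arm B. Each arm has 6 of 26 with a complication. The mean difference (A minus B) is 2 × (code for infectious − code for hemorrhagic) / 26. Over all 24 ways of numbering the categories 1 to 4, it runs from 2 × (−3)/26 = −0.23 to 2 × 3/26 = +0.23. The data are the same throughout; only the numbering changes.

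**2. Mean of a 0/1 code.** For delivery mode and ICU admission the mean is the proportion with the event, so the difference between means is the risk difference. The measure is valid for these two.

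**3. Chance of an empty arm.** P(at least one arm has zero events) = 1 − [1 − (1 − p)ⁿ]². For example, at p = 0.05 and n = 26, 0.95²⁶ = 0.264 and 1 − (1 − 0.264)² = 0.46.

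| Assumed rate | Expected events per arm, n = 26 | Empty arm, n = 26 | Empty arm, n = 30 |
|---|---|---|---|
| 3% | 0.8 | 70% | 64% |
| 5% | 1.3 | 46% | 38% |
| 10% | 2.6 | 12.5% | 8.3% |
| 20% | 5.2 | 0.6% | 0.2% |

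**4. What an interval for the risk difference shows.** Take 3/26 against 0/26. The odds ratio is infinite. The risk difference is 3/26 = 11.5 points. The Wilson limits are 4.0% to 29.0% for 3/26 and 0% to 12.9% for 0/26. Newcombe lower limit: 0.115 − √[(0.115 − 0.040)² + 0.129²] = −0.034. Upper limit: 0.115 + (0.290 − 0.115) = 0.290. Even 0/26 against 0/26 leaves about 13 points possible in either direction.

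**5. Which test.** The one-stratum Mantel-Haenszel statistic, without continuity correction, is (a − E)²/V. For 3/26 against 0/26, a = 3, E = 1.5 and V = 26 × 26 × 3 × 49 / (52² × 51) = 0.721, so the statistic is 3.12 and p = 0.077. Fisher's exact test gives p = 0.24. True size at nominal 5%, enumerating all tables at 26 per arm:

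| Rate | Mantel-Haenszel | Fisher |
|---|---|---|
| 3% | 0.7% | 0.01% |
| 5% | 2.2% | 0.1% |
| 10% | 5.0% | 1.0% |
| 20% | 4.7% | 2.3% |

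**The case against.** The strongest reply is that the plan is less deficient than the single phrase suggests. Most of it stands, and it sets the limits of this point.

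- A reader might infer that a mean difference is wrong for every categorical secondary outcome. It is not: for 0/1 outcomes it already is the risk difference. Only obstetric complications is left without a meaningful measure.
- A reader might infer that the plan offers only means or regression. It also names the Mantel-Haenszel test and linear trends, so a categorical test is available.
- A reader might infer that Mantel-Haenszel is unsuitable because there are no strata. With one stratum it is a Pearson chi-square scaled by (N − 1)/N. It can be computed with an empty cell, and its size is not materially inflated at these sample sizes. Small expected counts are a rule of thumb and do not mean excess false positives here. Its odds-ratio estimate does break down with an empty arm.
- A reader might infer that the models will fail. The documents give no event rates, an empty arm is uncommon at 10%, and it is very unlikely for a common outcome; if cesarean delivery is 20% or more, it is not a concern. Infinite odds ratios also presume a logistic link, which the plan does not name.
- The outcomes are secondary and partly exploratory, and confidence intervals are promised. But without a named measure and method, that promise does not fix what will be reported.
- Numeric birth weight and APGAR may exist in the hospital database that feeds Chart 5. The chart does not list them, so this cannot be confirmed.

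**Conclusion.** The point holds in a limited form. It is wrong as written for one outcome: a difference between means has no interpretation for the four complication categories, whatever the event rates. For the binary outcomes the measure is sound, but no test, effect measure or interval method is assigned and there is no rule for sparse data. If the regression is logistic, the lack of a finite estimate would be frequent at rates up to about 5%, occasional at 10% and negligible from 20%. Those probabilities assume equal rates in the two arms and 26 to 30 analysed women per arm. There is also a mismatch in the data: a mean gestational age cannot be computed from the three categories in Chart 5.

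This should be corrected, but it does not touch the primary outcome.

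**What to change.** - In secondary outcomes 1 and 2, analyse obstetric complications as any versus none and each type versus not.
- Report every binary outcome as a risk difference, telemedicine minus usual care, with a Newcombe or Miettinen-Nurminen 95% interval. State that interpretation rests on the interval and not on non-significance.
- Keep mean differences for numeric outcomes only. Record gestational age in weeks, and birth weight and APGAR as numbers, in Chart 5.
- In the Analysis plan, name the method for each outcome. The single-stratum Mantel-Haenszel (chi-square) test may stay. It should not be replaced by Fisher's exact test, whose heavy conservatism here would make a finding of no difference more likely.
- If an adjusted model is fitted to a rare outcome, Firth-penalised logistic regression is an option.

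The cost is slightly more analysis wording and a small change to the data form. The Trial status section places recruitment after ethics approval, so the change is easy to make before data exist.

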Data acquired according to this protocol will be stored in a password-protected database on a secure network. All entries will be made by an authorized member of the investigator's staff. Data will be entered into the study database and verified through the use of programmed edit checks for accuracy and completeness. The corrected data and a complete audit trail of corrections will be retained. An internal

audit of a sample of the data will be conducted quarterly to assure quality. The investigator will ensure that participants' anonymity is maintained. Participants will not be identified by their names, but by their assigned identification number and initials. Signed informed consent forms, will be maintained securely. Only authorized members of the investigator's staff will have access to the final trial dataset. All information regarding the study data or results supplied to the investigator is privileged and confidential information. The investigators agree to use this information to accomplish the study and will not use it for other purposes.

Safety management

The research team will be composed of a principal investigator, co-investigators and a trial statistician. A data monitoring committee is not required as the study management group will liaise every month to review interim analysis and monitor adherence. The principal investigator will make the final decision to terminate the trial in the event that uptake rates fall below pre-trial levels in either intervention arm. It is not anticipated that there will be premature ends of study. However, if this occurs, then the data will be analyzed and results circulated among the team members. The ethics committee will be notified of any premature termination and the reasons for termination. Adverse events or other unintended effects of trial interventions that come to the attention of trial investigators will be reported immediately to the study management Group. All protocol amendments will be submitted to the ethics committee for review and approval before implementation and to trial registries.

Trial status

This study protocol aims at disseminating and discussing a new model of prenatal care. It will be presented at the IRB of the Irmandade Santa Casa de Misericórdia de Porto Alegre and after approval the recruitment will start.

Dissemination policy

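### Secondary outcome 2 asks for mean differences in gestational age, birth weight, APGAR and ICU admission, but Chart 5 categorises the first, omits the next two and records the last as yes/no

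*Combined protocol and SAP*

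**What the plan says.** Under Outcomes, secondary outcome 2 is the "difference between means, between groups, of data related to the baby: gestational age at birth, birth weight, APGAR", with neonatal ICU admission as the fourth item in the same list.

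The text introducing Chart 5 gives the source of these data: "Clinical outcomes will be collected to explore the clinical effectiveness of the TPC based on hospital database reviews (Chart 5". Chart 5 has eight rows. Gestational age at birth is coded "preterm, term, post term". Newborn's size is coded "Small, appropriate, large for gestational age". Neonatal ICU is yes or no. The other five rows cover delivery method, maternal complications, breast-feeding, and later use of the obstetric and pediatric emergency services.

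For secondary outcomes, the Analysis plan offers, among other methods, "linear trends for ordinary categorical variables or multivariate regression models for categorical variables". It adds that "effect estimates will be presented with 95% confidence intervals".

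**The concern.** The outcome definition and the data list do not match. A mean difference in gestational age needs a number for each birth, and the chart keeps a category. A mean difference in birth weight or APGAR needs those values, and the chart has no place for them. ICU admission is recorded, but as a binary, for which a proportion by arm is the natural summary.

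At stake is whether the newborn outcome can be reported as defined. The Discussion hopes for similar effectiveness with no reduction in quality of care, and newborn outcomes are part of the evidence for that. Under Variables and data collection, medical students and residents collect the data, so the written item list matters. The APGAR minute is not stated either, so two abstractors could record different scores for the same baby.

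**Working it through.** The check is a comparison of texts. The plan gives no figure on this point to reproduce.

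**Step 1. Outcome against chart.**

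| Item in secondary outcome 2 | What the definition needs | What Chart 5 records | Result |
|---|---|---|---|
| Gestational age at birth | a number (weeks) | three ordered categories | too coarse for a mean difference |
| Birth weight | a number (grams) | no row | no data |
| APGAR | a score at a known minute | no row | no data |
| Neonatal ICU admission | yes/no | yes/no | recorded in full; a proportion, not a mean |

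Count: 1 recorded in full + 1 too coarse + 2 absent = 4.

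**Step 2. Does another part of the protocol supply the values?** Variables and data collection names four components: baseline, quality of life and economics, anxiety, and clinical outcomes. The only weight in Chart 1 is the mother's at her first appointment. Charts 2, 3 and 4 are GAD-7, EQ-5D and costs. Figure 2 has a single row for clinical outcomes with no items. APGAR appears elsewhere only in the Discussion, in a sentence about a cited study.

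**Step 3. Can the values be recovered from what is recorded?** Weeks cannot be rebuilt from three categories. Grams cannot be rebuilt from a small/appropriate/large label. There is nothing from which to rebuild APGAR.

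**Step 4. Does the Analysis plan close the gap?** A trend test or regression could compare gestational-age categories, but that is not the mean difference the outcome defines. Multiple imputation fills gaps in a recorded variable. It cannot supply one that was recorded for nobody.

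**Step 5. What coarsening could cost (illustration only).** Every input except the group size is my assumption: normally distributed gestational age, mean 39.0 or 39.5 weeks, SD 1.3, 1.5 or 2.0 weeks, cuts at 37 and 42 weeks, and a 1-week shift. The group size is the plan's 26 per arm.

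- Mean weeks, two-sided 5% t-test: power 78%, 65% and 42% for SD 1.3, 1.5 and 2.0.
- Linear trend test on the three categories (scores 1, 2, 3; 40,000 simulated trials per setting): about 27–41% if the shift is towards earlier birth, about 25–31% if towards later birth.
- 95% confidence interval half-width for the difference in mean weeks: 2.009 × SD × √(2/26) = 0.72, 0.84 and 1.11 weeks for the three SDs.

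The protocol does not posit a 1-week shift. These figures show only that categories carry less information than weeks. The mismatch in Step 1 does not depend on them.

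**The case against.** The strongest reply is that a row missing from a chart does not mean that data will be missing. The protocol names gestational age, birth weight and APGAR as outcomes directly below the chart, so an abstractor has that list too. The source is the hospital database, and a small/appropriate/large label is normally derived from birth weight and gestational age, so those values would probably be looked up anyway. Chart 5 is not called a case report form or said to be complete. The study database has its own fields, which the protocol does not list, and the appendices are not in the text available. All of this stands. It shows that the loss is conditional and avoidable. It does not make the two sections agree, and the chart's explicit coding of gestational age still conflicts with a mean in weeks.

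A reader might infer that these data are unobtainable or that secondary outcome 2 cannot be analysed at all. The documents support neither: the hospital record may hold every value, and gestational-age categories and ICU admission can be compared as they stand.

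A reader might also infer harm to the main result, because the opening design text couples clinical effectiveness with anxiety as primary. But the Outcomes section gives GAD-7 scores alone as primary, the sample size rests on GAD-7 ("A sample of 26 patients each group is needed to have 80% power"), and the clinical data are described as exploratory.

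**Conclusion.** The inconsistency is certain on the text. Abstraction exactly as Chart 5 lists the items would leave two of the four newborn items in secondary outcome 2 without data and a third unreportable as the stated mean difference. The fourth is complete but calls for a proportion. That this loss will occur is not established: it depends on staff recording only what the chart shows. With GAD-7 as the primary outcome, the point affects the completeness of a secondary outcome and introduces no bias into the primary comparison. It should be corrected because the remedy is small and values not captured at abstraction may be hard to recover later.

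**What to change.** Amend Chart 5 before recruitment, which has not begun: Trial status says that "after approval the recruitment will start". Add three fields:

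- gestational age at birth, in completed weeks and days;
- birth weight, in grams;
- APGAR at a stated minute, for example 5 minutes.

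Then align the Outcomes and Analysis plan sections with the data:

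- gestational age in weeks and birth weight in grams: mean difference with a 95% confidence interval;
- APGAR at the stated minute: between-arm difference with a 95% confidence interval, plus its distribution by arm;
- preterm/term/post term, derived from the recorded weeks, and neonatal ICU admission: counts and proportions by arm, not means.

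The cost is three more fields for about 60 births, taken from records already under review. No extra visits, new outcomes or larger sample are needed. The downside is that values may be missing for births at other hospitals, so the number available in each arm should be reported for each item.

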Superiority randomized controlled trial (RCT), comparing standard prenatal care and telemedicine prenatal care, with allocation ratio 1:1 and maximum follow-up 41 weeks (6 weeks pregnancy to 6 week postpartum) will be conducted. The primary outcome will be maternal anxiety and clinical effectiveness of both approaches. The SPIRIT guidelines (8) will be applied to assess the current RCT, and it is included in Appendices. A cost effectiveness study will also be conducted in the present study. The trial is registered to the International Standard Randomized Controlled Trial Number 48740621.9.0000.5335.

Setting

This study will be conducted at Santa Casa de Misericórdia of Porto Alegre - Santa Clara Hospital - Mario Totta Maternity (MTM), a teaching institution for residency and academic training in obstetrics. On average 3000 pregnant women attend prenatal care at MTM, by Brazil's Public Health System – the SUS (Unified Health System) every year, 14% of which are considered low- risk pregnancies. The MTM catchment area includes local, metropolitan and also regional population and has approximately 3000 deliveries per year.

Participants

The population of study includes every pregnant woman who seeks care in the obstetric outpatient clinics at Santa Casa antenatal care, by SUS and is classified as a low-risk pregnant. Those women who attend their first antenatal care at 6 to 12 weeks gestation at MTM using the public health system (SUS) will be screened for this study. We will classify low-risk according to the Brazilian Ministry of Health criteria, which includes patients that have no individual or social risk factors or history of previous obstetric complications, or any disease or condition that may interfere negatively in the pregnancy course (9). This criteria has been validated in several studies that had been carried out in Brazil, in which the prenatal care model is focused on well-being and safety of low-risk pregnant women (7) (10) (11).

Eligibility criteria

Inclusion criteria: Low-risk pregnant women, age between 18 to 34 years; gestational age less than 13 weeks at the first consultation and Portuguese native speaker.

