equal numbers in each arm by the end of the study. Blocks of varying length will be used to reduce the predictability of the allocation sequence. In advance of participant recruitment, an independent researcher will be responsible for generating the allocation sequence using the Stata program (version 2.0). Sealed envelopes will be used to assign participants to intervention groups. Thus, the allocation sequence will be concealed from all study researchers until the interventions are assigned, unless major adverse events or unexpected inconsistencies occur in the follow-up to the study.

Interventions

All eligible women who consent to participate in the study will be randomized into either usual prenatal care (UPC) or telemedicine prenatal care (TPC). The antenatal scheduling process will be similar between groups. In the UPC all appointments (at least 9) will be in person. Participants assigned to the TPC group will perform at least 6 in person appointments and 3 online appointments through the Google Meet platform; this group will have wearable for blood pressure and fetal heart home monitoring, as needed according to the guidelines defined previously by the Obstetric Outpatient Department. Consent for teleconsultation and medical device use at home will be obtained. In situations where Google Meet or internet isn't available, the appointments will be carried out by video call. Pregnant women from both arms of the study will receive standard care from the obstetric team. Clinical management will be based on evidence-based guidelines used at MTM, which is currently being revised to include remote antenatal care and will be finalized and available before collection of data. Santa Casa Hospital will provide all necessary laboratory and imaging tests. Participants from both arms of study will be advised to

10
seek obstetric emergency in case they are feeling some discomfort or pain, have any complications or need any further evaluations.

Variables and data collection

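### The per-protocol rule is a fixed count of attended sessions, so membership depends partly on pregnancy length and distorts the per-protocol birth outcomes; the intention-to-treat results are not affected

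*Combined protocol and SAP*

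**What the plan says.** The Analysis plan says the trial will have an "analysis by intention-to-treat and per protocol (at least 6 sessions attended"). This is the only definition of the per-protocol set. It stands in a general sentence about the trial, and nothing limits it to GAD-7. The economic analysis is separately tied to intention-to-treat.

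The sessions come from the section Interventions. For usual care, "In the UPC all appointments (at least 9) will be in person"; the telemedicine arm has "at least 6 in person appointments and 3 online appointments through the Google Meet platform", so nine as a minimum in each arm. Care starts in "pregnant women presenting for their first antenatal visit at 6 to 12 weeks of gestation" (Recruitment).

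Under Outcomes, secondary outcome 2 is "gestational age at birth, birth weight, APGAR, neonatal intensive care unit (ICU) admission". The same section says "Adherence to the proposed care will be assessed by attending the consultations", along with exams done and extra emergency consultations.

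The documents do not define a session, give no calendar of visits by week, and do not say how the count of six applies after an early birth or a pregnancy loss. Figure 2 also marks consultations in the puerperium.

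**The concern.** A count of attended visits is known only after randomisation, and for antenatal visits it is capped by how long the pregnancy lasts. A woman who keeps every appointment and delivers at 27 weeks can be classed as non-adherent, while one who skips three of nine and reaches term is classed as adherent. The rule then measures pregnancy length as well as adherence.

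For GAD-7 this is a poor adherence definition. For gestational age at birth it is selection on the outcome itself, and birth weight, Apgar and ICU admission follow gestational age closely. At stake are the per-protocol rates of preterm birth and ICU admission in each arm and, in some circumstances, the per-protocol comparison between arms. The Discussion hopes for similar effectiveness with no loss of quality, so a per-protocol contrast that had been shrunk could be read as support.

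**Working it through.** The plan gives no figure for the per-protocol set to reproduce. Its sample size enters only in step 5.

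**1. Inputs.** From the documents: threshold 6; nine planned sessions; first visit at week s, with s from 6 to 12. Follow-up is "maximum follow-up 41 weeks (6 weeks pregnancy to 6 week postpartum"), which agrees with antenatal care up to week 41: (41 − 6) + 6 = 41 weeks. Assumed: nine antenatal visits, evenly spaced.

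**2. When the sixth visit falls.** Visit k is at week s + (k − 1)(41 − s)/8.

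| Visit | s = 6 | s = 12 |
|---|---|---|
| 6 | 6 + 5 × 35/8 = 27.9 | 12 + 5 × 29/8 = 30.1 |
| 7 | 32.2 | 33.8 |
| 8 | 36.6 | 37.4 |
| 9 | 41.0 | 41.0 |

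A birth before about 28 to 30 weeks cannot qualify even with full attendance. After one missed visit, the sixth attended falls at 32 to 34 weeks; after two, at about 37 weeks.

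If one of the nine is a puerperal visit that counts, five antenatal visits are enough. With eight evenly spaced antenatal visits, the fifth is at s + 4(41 − s)/7, which is 26.0 to 28.6 weeks. The limit moves earlier but does not disappear.

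**3. Chance of qualifying when visits are missed.** Assume independent attendance of 85% per visit. P(at least 6 of n) is binomial: n = 9, 0.97; n = 8, 0.89; n = 7, 0.72; n = 6, 0.38; n = 5, 0. On the step 2 calendar, a birth between visits 8 and 9 (roughly term) has n = 8, a birth between visits 7 and 8 has n = 7, and one between visits 6 and 7 has n = 6.

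**4. Effect on rates and contrasts.** This was simulated with 400,000 women per scenario. Assumptions not in the documents: 10% preterm, 2% loss before 22 weeks, ICU risk rising as gestational age falls, and attendance of 70% to 100%.

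- Share kept, even schedule from week 10 to 40, 80% attendance: births before 28 weeks 0%, 28–31 weeks 23%, 32–33 weeks 52%, 34–36 weeks 66%, term 83%. At 100% attendance: 0%, 90%, 100%, 100%, 100%.
- Across four all-antenatal schedules (three even, one concentrated late) and all attendance levels, a preterm rate of about 10% becomes 3.4% to 9.8% in the per-protocol set. ICU admission of about 8.7% becomes 5.0% to 8.3%. With one puerperal visit counted, preterm becomes 6.7% to 9.9%.

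Between arms (even and late-concentrated schedules), preterm difference in percentage points, telemedicine minus usual care:

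| Scenario | All births | Per protocol |
|---|---|---|
| No true effect, 80% attendance in both | about 0 | about 0 |
| True 10% v 15%, 80% in both | 5.0 to 5.1 | 2.6 to 3.7 |
| No true effect, attendance 70% usual care v 90% telemedicine | about 0 | 2.4 to 3.1 |
| True 10% v 15%, attendance 70% v 90% | 5.1 to 5.2 | 6.6 to 6.9 |

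In the third row the false ICU difference is 1.2 points and the false difference in gestational age is −0.22 weeks.

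**5. Scale in this trial.** At an assumed 10%, 60 women give about 6 preterm births. Using the retention at 80% attendance for 32–36 weeks, the rule removes 6 × (0.83 − 0.66) = 1.0 to 6 × (0.83 − 0.52) = 1.9 more women than if those births were kept at the term rate. The 95% half-width for a difference between two 10% rates is 1.96 × √(2 × 0.1 × 0.9/n): 15 points at n = 30 per arm and 16 points at n = 26.

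**The case against.** The strongest reply is that intention-to-treat is named first, the primary outcome is GAD-7, and the economic analysis is by intention-to-treat. An unaffected result for every birth outcome will therefore exist. The distortion is also far smaller than the sampling error in step 5. Both points stand, and they keep this from being a major defect. They do not justify planning an analysis with a known and avoidable selection on the outcome.

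It can also be said that the plan never states which secondary outcomes get a per-protocol analysis. That is true; but the sentence is general and nothing excludes the birth outcomes, so the plan as written permits it.

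Two stronger readings are tempting and go too far:

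- A reader might infer that the rule simply removes women who deliver early. It does not. Removal is graded: late preterm births with full attendance qualify, and only births before about 28 to 30 weeks are shut out on the assumed calendar. A counted puerperal consultation softens this further, and so would more than nine visits. Pregnancy losses also fail the count, but they have no neonatal outcome to bias.
- A reader might infer that the rule always pushes the arms towards similarity. With equal attendance it shrinks a true difference. With unequal attendance it can create a difference or enlarge a true one. With equal attendance and no true effect it does nothing to the contrast.

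**Conclusion.** The point holds for the per-protocol analysis of birth outcomes, as a minor to moderate issue. That membership depends on gestational age follows from the plan's own rule and its nine planned sessions. The size does not: it rests on an assumed calendar, attendance and preterm rate. Under those assumptions, per-protocol preterm and ICU rates are shifted downwards in each arm, from slightly (9.8% against about 10%) to markedly (3.4%). The contrast moves by about 1 to 3 points when gestation or attendance differs by arm. Different attendance is plausible, since the arms differ in visit format, but the documents give no attendance figures. The intention-to-treat results and the economic analysis are not affected.

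**What to change.** State in the Analysis plan that gestational age at birth, birth weight, Apgar, neonatal ICU admission and delivery mode are reported by intention-to-treat only, and that the per-protocol analysis is limited to GAD-7. This costs a sentence and removes the bias in the birth outcomes whatever the visit calendar turns out to be. The Trial status section places recruitment after ethics approval, so it can be settled before data exist.

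For the GAD-7 per-protocol set, preferably replace the count by a share of the sessions that fell due while the woman was still pregnant; two thirds keeps 6 of 9. This is secondary and costs more. The sponsor must state which visits count as sessions (in person, online, puerperal, emergency) and when they fall due, and must count those due for each woman. The documents say attendance will be assessed but not that visit dates are recorded, so that should be confirmed. A share also admits a woman with very few visits before an early loss, so the sponsor should say how such cases are handled.
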